19. **Budget:** Response: Critical reviewers have raised concerns over the accuracy of the real time recordings. The DVD recording (e.g. biopsy duration, polypectomy durations etc) provides more objective and "accurate" measurements. Nevertheless, we have made adjustment (reduction) to the expenses for the study.

20. **Overall Evaluation:** Response: The clinical implication is detection of more adenomas may translate into fewer missed but potentially precancerous lesions. The revised application has added preliminary data to address the Reviewer's concerns.

Critique 3

Statistics

1. Response: The revised application involves a single colonoscopist and enrollment of only first time screening colonoscopy patients. The statistics section has been revised accordingly.

2. Response: see response above.

3. Response: The statistical analysis has been entirely rewritten. We investigate the primary hypothesis through logistic regression models. To follow up, we investigate how covariates affect the rate of adenoma detection. Our secondary analysis uses repeated measures regression models to investigate how secondary outcomes (adenoma size, adenoma location, etc) vary between the three methods.

4. Response: Because patients are sedated, and will be given additional sedation medication throughout the procedure if requested, we do not expect large numbers of drop-out (failure to complete colonoscopy). However, patients that do drop out will be retained and assigned a value of zero for the number of adenomas detected, if none is found in the examined segments.

5. Response: The analyses are designed to quantify the differences between the three treatment groups and to determine if they are significant. Additionally, we plan to account for the rate of colorectal cancer diagnoses in the estimation of the differences between the three tests.

Specific Aims

(a) Goal

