Population studies showed that traditional air colonoscopy failed to eliminate post screening colonoscopy cancers or cancer mortality in the proximal colon. Even diminutive adenomas harbor significant dysplasia. A simple, inexpensive, easy-to-learn method of adding indigocarmine to the water method may increase the yield of proximal diminutive adenomas. A higher ADR may minimize the burden of interval CRC by decreasing missed adenomas. The current study evaluates the benefits of a combined chromoendoscopy and water method for screening colonoscopy in identifying proximal diminutive adenomas compared to the water method alone and the conventional air method. The long term goal is to perform further studies to determine if post screening colonoscopy interval cancers and cancer mortality in the proximal colon can be attenuated among the veteran population by the novel methods.

(b) Hypothesis

In patients undergoing optical colonoscopy for first time CRC screening, a higher proximal diminutive ADR (proportion of patients with at least one diminutive adenoma in the colon proximal to the splenic flexure) will be found in the group examined by combined chromoendoscopy (indigo carmine) with water method compared with water method alone or air method.

Primary outcomes: Proximal diminutive (<10 mm) adenoma detection rate.

Secondary outcomes: ADR (overall for entire colon and for proximal colon), cecal intubation success rate, sedation medications.

Co-variables: patient demographic variables [age, gender, BMI, co-morbidity, endoscopic findings, etc.], successful completion of split bowel preparation

(c) Specific Objectives

To compare the primary and secondary outcomes in a prospective RCT involving the combined chromoendoscopy with water method vs. water method alone and air method in asymptomatic patients undergoing first time outpatient screening colonoscopy.

Short title: Comparative efficacy of water & indigo carmine vs. water or air method on ADR – a RCT

Long title: RCT to compare proximal diminutive adenoma detection rate (ADR) of combined chromoendoscopy (Indigo carmine) with water infusion in lieu of air insufflation (water method) vs. water method alone or conventional air method in screening colonoscopy

(1) Rationale

Statement of the Problem

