If the cecum is believed to have been reached, but the usual landmarks are not recognizable, more water is infused to distend the cecum to aid visualization of the appendix opening. The volume of infused water, the use of position change and abdominal compression will be recorded. Once the appendix opening is visualized, air insufflation will be used to distend the cecum to confirm touching of the cecal floor with visualization of the ileocecal valve and/or the appendix orifice (cecal intubation). Thereafter, usual air insufflation will be used to facilitate suctioning of residual colonic content (mostly water and residual feces) and mucosal inspection, biopsies or polypectomy during endoscope withdrawal. All polyps (including diminutive ones in the right colon) will be removed and tissue submitted for pathological evaluations. When multiple diminutive polyps (predominantly hyperplastic) in the rectum are identified and recorded; a limit of one biopsy will be taken (to minimize time burden on study subjects).

Reassuringly, water enemas using equivalent volumes were not associated with significant fluctuations in serum electrolytes [63]. Preliminary data did not show any significant change or differences in the serum electrolytes level before and after the water infusion (Table 8) [58]. With the suction of dirty water and then infusion of clean water during scope advancement, the actual amount of water within the colon at any time during scope insertion is much less than the total volume of water used to facilitate scope passage.

The combined chromoendoscopy with indigo carmine and water method: As used in pilot study, the technique is identical to the water method above except we add 10 ml of 0.8% indigo carmine solution into a liter bottle of sterile water to make up a solution of 0.008% indigo carmine [22].

b. Population to be studied

Inclusion criteria: asymptomatic veterans scheduled for first time screening colonoscopy and agree to be randomized will be enrolled.

Exclusion criteria: patients who decline to be randomized, non screening cases.

c. Unit(s) of analysis (Table 10).

Table 10: Primary and secondary outcome variables

Measures	Details
Primary Outcome	
Proximal diminutive adenoma	1 = yes, 0 = no
Primary covariates	
Demographic variables	Age, gender, BMI, ethnicity
Volume of water (ml)	ml used during colonoscopy
Cecal intubation time*	Time from anus to cecum (appendix opening, ileocecal valve seen)

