Withdrawal time*	Time from cecum to anus
Total procedure time*	From insertion of colonoscope to removal from the anus
Completion of split preparation	Yes = 1, no = 0
Secondary covariates	
Colon cancer	Colon cancer discovered during exam (Yes = 1, no = 0)
Sedation medications	Type, initial dose, additional doses during colonoscopy based on patient pain score and request
Secondary Outcomes	
Size of adenoma*	mm measured by open forceps
Anatomical location of adenoma	rectum, sigmoid, descending, splenic, transverse, hepatic, ascending, cecum
Located behind a fold*	Yes = 1, no = 0
Morphology of lesion*	Polypoid or flat
Pathologic diagnosis of the biopsy or snared polypectomy specimen	Adenoma (with or without advanced features), hyperplastic polyp, serrated adenoma
Immediate complications	Perforation, bleeding, hypoxia, hypotension, arrhythmia
Complications up to 30 days	Perforation, bleeding, hypoxia, hypotension, arrhythmia, severe abdominal pain requiring ER visit and/or admission to hospital

* Documented during colonoscopy and objective confirmation by digital video record of endoscope clock.

Record keeping: A digital image capturing system will be used to record the procedure to document the procedure times (insertion, arrival in the cecum, biopsy, polypectomy, end of examination), confirmation of cecal intubation (visualization of the appendix orifice and/or the ileocecal valve) and the findings during the withdrawal phase (recorded by the research assistant). The digital images will bear no personal identifier.

d. Sampling strategy

[figure not shown]
The consent covers agreement to allow the colonoscopist to randomize the method to aid colonoscope insertion and examination (chromoendoscopy with water vs. water method vs. air insufflation), and to video record and photograph the procedure for analysis.

In order to accommodate the patients and allow them time to complete the split bowel preparation in the morning of the procedure, the study procedures will be scheduled as late morning and early afternoon cases as this will give the patients more time to complete the bowel preparation.

Sample size calculation

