Demographic data interview & record review (co-variables)	X		
Medical and surgical history (co-variables)	X		
Complications - emergency department visit, hospitalization (co-variables)			X

(g) General analytic plan (statistical analysis):

Primary Hypothesis.

In patients undergoing sedated colonoscopy for screening, when all polypoid and flat lesions including diminutive ones proximal to the splenic flexure are removed by polypectomy or biopsy, the patients examined by the combined chromoendoscopy and water method will be found to have a higher proportion of individuals with at least one proximal diminutive adenoma compared with the water method alone or air insufflation method for aiding insertion of the colonoscope.

Statistical Analysis: We will summarize the variables collected by calculating the frequencies of the categorical variables [such as number of patients with at least one proximal diminutive adenoma (proximal diminutive ADR), number of adenomas detected, adenoma location, adenoma size, gender, ethnicity, etc) and calculating the mean and standard deviation of the continuous variables (such as adenoma size, volume of water used, age, BMI, etc)].

To investigate differences in ADR, we will use logistic regression models, with an outcome that is a binary variable denoting whether each subject had one or more diminutive proximal adenomas. These models will allow us to quantify the differences between the three tests and determine if the differences are statistically significant. We will account for demographic characteristics (age, gender, BMI, ethnicity, etc) and investigate how other primary covariates (procedure time, volume of water used in study, etc) affect the rate of adenoma detection. Following, we will investigate the effects of secondary covariates (colon cancer detected, sedation medications) on adenoma detection rates.

As a secondary analysis, we will investigate how the secondary outcomes vary among the three tests. We will use repeated measures ANOVA and logistic regression models to quantify the differences between tests and to determine if they are statistically significant.

Pitfalls and solution

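### Repeated measures ANOVA is named for the secondary outcomes but does not fit the lesion features in Table 10, several of which exist only for detected lesions and have no all-patient version

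*Combined protocol and SAP*

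**What the plan says.** Section (g) covers all secondary outcomes in one sentence: "We will use repeated measures ANOVA and logistic regression models to quantify the differences between tests and to determine if they are statistically significant". It gives no unit of analysis, within-patient factor, clustering term or analysis set for them.

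The Response to reviewers (Critique 3, Statistics, item 3) words the method differently and names its targets: "Our secondary analysis uses repeated measures regression models to investigate how secondary outcomes (adenoma size, adenoma location, etc) vary between the three methods".

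There are two lists of secondary outcomes. Specific Aims (b) gives outcomes with one value per patient: "ADR (overall for entire colon and for proximal colon), cecal intubation success rate, sedation medications". Table 10 gives lesion features together with complications. The lesion features are:

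- size in mm
- anatomical location ("rectum, sigmoid, descending, splenic, transverse, hepatic, ascending, cecum")
- located behind a fold (yes/no)
- morphology (polypoid or flat)
- pathology ("Adenoma (with or without advanced features), hyperplastic polyp, serrated adenoma")

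Under Randomization, each patient is allocated to one of three parallel arms.

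**The concern.** Repeated measures ANOVA needs a continuous response observed at the levels of a within-patient factor. Table 10's lesion features do not have that structure, so the named method cannot be applied to them as written.

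The second difficulty is what a comparison of these features would mean. A lesion has a size, shape or position in the dataset only if it was found, and the trial is built on the expectation that the arms find different lesions. The patients contributing lesion data are therefore selected after randomisation, and selected differently by arm. A smaller mean size or a larger flat share in the dye arm could simply reflect that more small and flat lesions were found. At stake is a secondary result read as a separate effect of the method.

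**Working it through.** The plan gives no figure of its own on this point. The check is a comparison of method with data, followed by a count of who contributes.

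**1. Method against data type.**

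| Table 10 feature | Type | Repeated measures ANOVA | Logistic regression |
|---|---|---|---|
| Size (mm) | continuous, 0 to several per patient | no fixed repeated factor, unequal numbers | no |
| Location | 8 nominal categories | no | not in binary form |
| Behind a fold | binary | no | in form; no clustering stated |
| Morphology | binary | no | in form; no clustering stated |
| Pathology | nominal | no | not in binary form |

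Method is not a repeated factor, because each patient has one method. Pain is scored repeatedly during the procedure, but Table 11 carries its maximum as a quality measure, not as a secondary outcome.

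**2. Which features already have a per-patient version.** Overall ADR and proximal ADR (Specific Aims (b)) are yes/no per patient. So is the primary outcome, which combines the <10 mm cut, proximal location and adenoma histology. No such version is defined for size in mm, behind-a-fold, flat morphology, segment-level location or pathology subtype. The drop-out rules (Critique 3, item 4; Other issues, differential dropout) set a zero adenoma count or a treatment failure. They do not give a value for these features.

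**3. Patients with no adenoma, hence no adenoma size or location.** With 110 randomised per arm (Sample size calculation), the expected number is 110 × (1 − overall ADR), taken at the highest and lowest ADR in the documents.

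| Arm | Overall ADRs in the documents | Result |
|---|---|---|
| Air | 26% (Table 3), 27% (Table 4), 46% (collaborator site, Rationale) | 110 × 0.54 = 59.4 to 110 × 0.74 = 81.4 |
| Water | 35% (Table 4), 37% (Table 3), 40% (Table 6), 48% (Table 7), 57% (collaborator site) | 110 × 0.43 = 47.3 to 110 × 0.65 = 71.5 |
| Dye + water | 62% (Table 6), 79% (Table 7) | 110 × 0.21 = 23.1 to 110 × 0.38 = 41.8 |

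**4. Expected difference between arms in who contributes.** At the planning rates of 14%, 34% and 64%, the patients with a proximal diminutive adenoma would number 110 × 0.14 = 15.4, 110 × 0.34 = 37.4 and 110 × 0.64 = 70.4. Sections (e) and Pitfalls and solution say that dye and water bring out small and flat lesions in particular, and size and morphology are among the features to be compared.

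**5. How the denominator changes the picture.** In the collaborator-site data (Rationale), proximal ADR was 35% (air) and 46% (water), and for adenomas under 10 mm it was 25% and 38%. Patients whose only proximal adenomas were 10 mm or larger are therefore 35 − 25 = 10% and 46 − 38 = 8% of all patients. Among patients with a proximal adenoma they are 10/35 = 29% and 8/46 = 17%. This illustrates the mechanism only. It is a patient-level subset that the trial does not plan to test. Back-calculated counts of about 19/67 and 14/81 give a Fisher p of about 0.12.

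**The case against.** The strongest reply is that the point concerns wording on exploratory outcomes. Critique 2, item 5 narrows the secondary outcomes to overall ADR, cecal intubation and sedation, and item 6 treats additional observations as hypothesis-generating. For those core outcomes the repeated-measures label is inapplicable but does little harm. This stands, and it limits the severity. It does not remove the point, because Table 10 and Critique 3, item 3 still call lesion features secondary outcomes and section (g) plans significance tests.

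A reader might also infer more than the documents support:

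- **That no all-patient version of any lesion feature exists.** Overall ADR, proximal ADR and the primary outcome are such versions for location, histology and the <10 mm cut.
- **That type I error is inflated by a known amount.** That would require clustering to be ignored, whereas both wordings signal within-patient repetition. The documents give no intraclass correlation and no lesion count per patient for this population.
- **That the model for size is contradictory because size appears twice in section (g).** It is listed among the categorical variables ("number of adenomas detected, adenoma location, adenoma size, gender, ethnicity, etc") and again under "calculating the mean and standard deviation of the continuous variables (such as adenoma size, volume of water used, age, BMI, etc". Both belong to the descriptive summary, and tabulating size classes as well as a mean is ordinary practice.
- **That the rectal biopsy limit undermines the adenoma data.** The rule reads: "When multiple diminutive polyps (predominantly hyperplastic) in the rectum are identified and recorded; a limit of one biopsy will be taken". It leaves some rectal lesions without pathology, but it concerns mainly hyperplastic polyps and has little bearing on adenoma features.

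The no-adenoma counts would be the same under any model. They show how many patients fall outside a lesion-level comparison, not the harm done by naming ANOVA.

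**Conclusion.** The point holds, as a minor one. The named ANOVA does not fit the Table 10 lesion features, and the planned lesion-level tests are not limited in interpretation to detected lesions. Five features lack a version covering all randomised patients: size in mm, behind-a-fold, flat morphology, segment-level location and pathology subtype.

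About 59–81 (air), 47–72 (water) and 23–42 (dye + water) of 110 patients per arm would contribute no adenoma size or location. These ranges assume that the trial's overall ADRs fall within those reported in the documents. The sources are mixed: Table 3 includes surveillance and diagnostic cases, and Tables 6 and 7 are small. How far detection alone would move a lesion-level test depends on lesion sizes and counts that the documents do not give, so no bias or error rate is stated.

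The documents do not say that the investigators will read a lesion-level difference as a separate effect. The plan leaves that reading open. The primary analysis, a per-patient logistic regression, is unaffected.

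**What to change.** In section (g), replace repeated measures ANOVA with named models:

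- **Once-per-patient outcomes, all randomised patients:** logistic regression for overall ADR, proximal ADR and cecal intubation; one-way ANOVA/ANCOVA or a rank method for sedation dose.
- **Lesion features:** GEE or mixed models clustered by patient, linear for size and logistic for behind-a-fold and morphology. Location and pathology should be multinomial or descriptive only. Label all of these as describing detected lesions.
- **Arm comparisons of a lesion feature, where wanted:** a per-patient yes/no version, such as at least one flat adenoma, with all randomised patients as the denominator. This still measures detection, but on the randomised groups.

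Reconcile the wording in Critique 3, item 3 with section (g). The cost is analysis-plan text and minor programming; the data are already to be collected.

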Ransibrahmanakul K, [name], Mann SK, Siao-Salera R, Lim BS, Hasyagar C, Yen D, Nastaskin I, Leung FW. Comparative effectiveness of water vs. air methods in minimal sedation colonoscopy performed by supervised trainees in the US -- a RCT. *Am J Clin Med* 2010;7(3):113-118.

Leung FW, [name], Siao-Salera RM, Mann SK, Guy Jackson G. The water method significantly enhances detection of diminutive lesions (adenoma and hyperplastic polyp combined) in the proximal colon in screening colonoscopy - data derived from two RCT in US veterans. *J of Interv Gastroenterol*. In press, 2011.

[name], Ransibrahmanakul K, Toomsen L, Mann SK, Siao-Salera RM, Felix W, Leung FW. The water method combined with chromoendoscopy enhances adenoma detection. *J of Interv Gastroenterol*. In press, 2011.

Leung FW, [name], Mann SK, Friedland S, Ramirez FC. Innovation Forum - The water method significantly enhances the outcome of colonoscopy in sedated and unsedated patient. *Endoscopy*. In press, 2011.

Human Subjects

(1) Risk to Subjects

(a) Human Subjects Involvement and Characteristics: Risks common to all forms of colonoscopy (sedated or unsedated, irrespective of the clinical study) include: pain, bloating, medication reaction, bleeding, perforation, intravenous site reaction and rarely death. Sedated colonoscopy has a 1.1% risk of cardiopulmonary events (hypotension, hypoxia, arrhythmia). Death occurs in less than 0.003%.

Inclusion criteria: asymptomatic veterans scheduled for routine screening colonoscopy and agree to be randomized will be enrolled. Exclusion criteria: patients who decline to be randomized, emergent colonoscopy, evidence of colonic obstruction based on pre-colonoscopy clinical evaluation, previous history of colonic operations, hemostasis procedure, surveillance of inflammatory bowel disease, unable to give consent. Other exclusion criteria were current participation in other studies, a history of colonic surgery, a medical condition that could increase the risk associated with colonoscopy (active cardiac or pulmonary disease or other serious disease) or that would preclude a benefit from colonoscopic screening (cancer or any terminal illness), a prosthetic heart valve, anticoagulant therapy, nonmedical problems (psychiatric disorders, lack of transportation, homelessness or lack of support at home, or excessive use of alcohol), and a need for special precautions in performing colonoscopy (i.e., antibiotic prophylaxis).

(b) Sources of Material: The patients' existing medical records in CPRS which contain demographic data such as age, sex, identification number, list of associated medical illnesses, medications will be reviewed. The patients' responses to the questionnaire designed for this study, the results of colonoscopy and pathology reports are specific information obtained for research purposes.

(c) Potential Risks:

Risks related to the clinical study:

Questionnaire: Inconvenience, embarrassment about revealing feelings related to the colonoscopy.

Other risks: Potential risks include confidentiality risk regarding medical and personal information. A breach of confidentiality is not anticipated due to the security procedures for research data.

Physical Risks: Water infusion in lieu of air insufflation has no known physical risks. Blood draw for checking serum electrolytes may be associated with pain and bruising at the puncture site and minimal risk of infection. Indigocarmine may be associated with nausea and itchiness but there is no reported side effect in previous studies involving the use of indigocarmine as dye staining in colonoscopy.

Psychological Risks: Water infusion in lieu of air insufflation has psychological risks of anxiety.

Social Risks: Water infusion in lieu of air insufflation has no known social risks.

Economic Risks: Water infusion in lieu of air insufflation has no known economic risks.

(2) Adequacy of Protection from Risks

(a) Recruitment and Informed Consent: For recruitment, the following will be presented to all patients attending pre-colonoscopy education class or by mail. Patients will be informed of the study and control methods of sedation and the use of water infusion in lieu of air colonoscopy with dye (study method) or without dye (study method) or conventional air colonoscopy (control method). The doctors will be conducting a study to determine if the study methods have any advantage over the control method. All patients who present to their scheduled elective colonoscopy will be invited to participate.

Participation will involve giving consent to be assigned in a random manner (according to a random list of codes generated by the computer) to one of the three ways of undergoing the examination. There will be questionnaires to be answered by all the participants.

(b) Protection against Risk:

Minimizing risks through study design:

Risk from time spent in responding to questionnaires: All questionnaires will be kept as concise as possible to minimize the time required to complete them.

Risk from discomfort associated with colonoscopy: Experienced endoscopists will perform and trained personnel will assist in the performance of the colonoscopy.

In addition, the following measures will be implemented to minimize risks for the subjects:

1. Enrollment of subjects will adhere to the inclusion and exclusion criteria.

2. The subjects will be given instructions to notify the study personnel if they have any concerns or untoward symptoms. They will be given the name and phone number of the site investigator and coordinator. An alternative number to one of the research team members will be given to subjects if they are not available. If an adverse event associated with the study should occur, the patients can contact one of the research team members, who will arrange appropriate and timely evaluations.

3. Subjects will be informed of new findings that may affect their decision to remain in the study.

4. VA good clinical practice guidelines will be followed.

5. VA information security measure will be implemented: Written documents and records will be coded so that the identity of the patient is protected. When not in use by the research team, these documents, records and codes will be placed in a locked file cabinet. Key access is available to members of the research team only. All computerized data will be placed in password protected computers. Password access will be available to members of the research team. These procedures are likely effective in protecting confidentiality.

(3) Potential benefit of the Proposed Research to the Subject and Others.

There are no known benefits to the research subjects.

(4) Importance of the Knowledge to be gained.

The result of the study may reveal if the additional dye staining (chromoendoscopy) is more or less efficacious, or no difference compared with the water method or the conventional air method in terms of finding more lesions (polypoid or flat lesions - hyperplastic and adenomatous polyps or cancers).

Therapeutic alternatives: All subjects in the study method group can undergo colonoscopy using the conventional air method.

Risk/Benefit analysis: The risks for both groups are time spent in responding to questionnaires. The potential benefits for society are that we will gain RCT data to support or not the use of water infusion (with or without dye staining) colonoscopy performed for colorectal cancer screening.

Comprehension of the information provided: Only subjects who can read and understand the consent are enrolled. The consent form will be provided to the patient in advance of the colonoscopy (e.g. by mail, as handout at the time of pre-colonoscopy class) to enable the patient to have time to read over the descriptions, to seek other opinions and to discuss with family members or friends. The subject is asked questions and feedback is elicited to ensure that the subject is aware of the consent including risks and benefits. The questions are as follows:

Directions: Make a subjective judgment regarding item 1 below. Ask the patient question 2 through 7. The evaluator may select the appropriate language to use in formulating the questions in order to assist the subjects' understanding.

Questions:

1. Is the subject alert and able to communicate with the examiner? Yes No

2. Ask the patient to name at least two potential risks incurred as a result of participating in the study.

3. As the patient to name at least two things that will be expected of him/her in terms of patient cooperation during the study.

4. Ask the patient to explain what he/she would do if he/she decides that they no longer wish to participate in the study.

5. Ask the patient to explain what he/she would do if he/she is experiencing distress or discomfort.

6. Ask the patient if participation in this research is voluntary. True False

7. Ask the patient whether he/she could get a second opinion regarding his/her care because his/her doctor is also a researcher and these two roles can be in conflict sometimes. True False

I hereby certify that the above patient Is, Is Not, able to communicate and able to give acceptable answers to items 2, 3, 4, 5, 6 and 7 above.

Evaluator

Date

Information withheld from subjects: None

Inclusion of women and minority: Every effort appropriate to the settings will be made to include women and minority in this study.

(5) Safety and Monitoring.

This study is a MODERATE risk clinical project with the potential of uncommon serious adverse events or unanticipated problems involving risks to participants.

The study methods both utilize water infusion in lieu of air insufflation with sedation, with the addition of dye to the combined chromoendoscopy and water method. Indigocarmine has been used and recommended in the literature for chromoendoscopy to enhance detection of colon polyps.

Exclusion criteria for safety include patients who decline to participate, unable to give informed consent or complete the questionnaires due to language or other difficulties.

All patients will be seen by one of the site investigators or the research staff prior to enrollment.

After participant enrollment, one of the site investigators will review blood pressure, cardiac rhythm and pulse oximetry (oxygenation) safety parameters prior to participant enrollment.

A study physician will be available on site for managing adverse events.

The site investigators will monitor study subjects for adverse events during the study.

Monitoring for pain in both study and control method groups will be carried out as follows: During the examination (with the colonoscope tip in the rectum, sigmoid colon, splenic flexure, transverse colon, hepatic flexure, ascending colon and cecum) or at 2-3 minute intervals, the patient will be asked to report pain on 10 point scale (0 = no pain, 10 = maximum pain) and for those who receives sedation, patient will be asked if additional medications are needed for control of pain. Additionally, if a pain score of ≥ 2 is recorded, medications will be offered. In either instance, the patient can decline or accept the medication depending on whether the pain is tolerable or not.

Monitoring for blood pressure, cardiac rhythm and pulse oximetry (oxygenation) will be maintained throughout the entire colonoscopy. Devices with automatic alarms used on a routine basis for all colonoscopy patients will be employed. Any alarm signals will be attended to immediately by a member of the research team and appropriate action will be taken to resolve any safety issues.

The identity of the subjects will be coded so that the data sheet with patient information will be de-linked from the patient identification. The coded video recording does not contain any patient identifier. The code will be kept in separate locked location and password access-protected computer (shared drive on the VA computer). When not in use by member of the research team all hard copies of coded patient information will be locked in file cabinet in designated location with locked access (e.g. investigators' office). All patient data transferred to computerized spread sheets will be stored in computers protected by password. Password access will be available to members of the research team only. At designated time after completion of the study (e.g. after publication of results), all stored data will be destroyed or erased. These measures are taken to comply with HIPAA requirements. The site investigators will review any complications and bring the occurrence to the attention of the Institutional Review Board.

Description of how adverse events are graded:

The main interventions are conventional method versus study methods. A grading scale will be used to describe adverse events if the need arises: 1=mild, 2=moderate, 3=severe, 4=life-threatening, 5=fatal. The attribution scale is 1=definitely not related, 2=probably not related, 3=possibly related, 4=probably related, 5=definitely related to the study interventions.

Plan for adverse event reporting:

The site PI will review all adverse events.

The site PI will promptly report any serious adverse events or unanticipated problems involving risks to study subjects in accordance with regulations: reportable adverse effects arising from any research procedures will be submitted promptly to the IRB. Although they are not anticipated to occur, deaths will be reported within 24 hours to the IRB. Unanticipated problems or Serious Adverse Events in research subjects will be reported to the IRB within 5 working days of awareness of the event and written reports will be submitted to the IRB no later than 15 calendar days after the event.

All reportable adverse events will be compiled, and reported in summary form, on an annual basis to the IRB, and at the conclusion of the study.

Performance and frequency of safety reviews:

The site investigators will perform safety reviews for all patients enrolled in this study on a weekly basis. The site PI of the study is responsible for carrying out continuous monitoring of accrual, data quality, and adverse events. The local study monitoring team will review the accumulating data regarding overall safety and efficacy of treatments employed in the trial. The study monitoring team will meet (twice a year) to review adverse events and subject safety issues.
